4.2 SECONDARY OUTCOMES

Secondary outcomes include neuroimaging, cognitive (neuropsychological assessments), gait and mobility outcomes including incidence of fall, blood biomarkers, quality of life scorings, as described in our primary and secondary hypotheses. Secondary outcomes are described in detail in Section 7.

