5. STUDY POPULATION

5.1 PARTICIPANTS, RECRUITMENT, STRATIFICATION, AND BLINDING

We will target older adults aged 60 and over with MCI. Interventions will be done across five sites: London (lead and sponsor site, target recruitment: 70 participants), Waterloo-University of Waterloo (target recruitment: 25), Waterloo-Wilfrid Laurier University (target recruitment: 20), Montreal (target recruitment: 30) and Vancouver (target recruitment: 55). Each intervention site may have more than one recruitment center. For those who are interested in participating, a consent and screening session will be arranged as described in our participant flowchart, Figure 3.

Once informed consent is obtained, we will perform the screening tests. Those who remain eligible after the screening session including the Physical Activity Readiness Questionnaire Plus (PARQ+) and who provide written recommendation from their physician or site physician indicating their appropriateness to participate in an aerobic-based exercise training program will proceed to baseline assessments. Participants will be informed that they will be randomly assigned to one of five arms by the research coordinator and will be blinded to the investigators' hypothesis as to which is the preferred intervention arm.

All groups will have an equal volume and frequency of contact with trainers over the 12 months of the study. All primary and secondary outcomes will be obtained and analyzed by blinded assessors on different days to the training programs.

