6.3 Supervision

All physical exercise training will be fully supervised by research assistants trained in exercise physiology or with kinesiology or physical therapy backgrounds or training. Training frequency is 3 days/week. Each session will take 90 minutes on average.

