7.2.2 BLINDING

In order to minimize a source of bias, this trial is planned to be a double-blinded study. Research personnel performing the outcome assessments will be blinded to group allocation. Participants will be blinded of intervention.

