7.4 TELEPHONE FOLLOW-UP (9 MONTH POST-BASELINE TESTING)

Three months after the end of the intervention, a telephone follow-up will take place to document any falls that have been recorded on the participants' falls calendar. This will be done by the study Site Coordinator or Research Assistant.

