APPENDIX I

Procedure	Visit 1 Screening	Visit 2 Baseline	Randomization	Visit Table		
				Visit 3 6M Visit	Telephone Follow-up (9M post-Baseline)	Visit 4 12M Visit
Written Informed Consent	X					
Demographic Information	X					
PASE Questionnaire	X			X		X
Mini Mental State Examination (MMSE)	X					
Montreal Cognitive Assessment (MoCA) Logical Memory 1 & 2 *	X			X		X
CERAD Word List Recall *						
Geriatric Depression Scale (GDS-30)	X			X		X
Generalized Anxiety Disorder 7 (GAD-7)	X			X		X
Clinical Dementia Rating (CDR)	X			X		X
Physical Activity Readiness Questionnaire Plus (PAR-Q +)	X					
ADCS-ADL and IADL	X			X		X
Clinical Medical Questionnaire		X		X		X
Dual Task Control Assessment		X		X		X
Six Minute Walk Test (6MWT) ^		X		X		X
Quality of Life Questionnaire (SF-36)		X		X		X
ADAS-Cog 13 (+ tests **)		X		X		X
Digit Span Forward and Backward WAIS-III **		X		X		X
TMT A and B **		X		X		X
Digit Symbol Test **		X		X		X
Boston Naming Test **		X		X		X
Colour Word Interference Test		X		X		X
Envelope Test		X		X		X
Short Physical Performance Battery (SPPB)		X		X		X
Gait Assessment using Gait Mat and accelerometers (when available)		X		X		X
Neuroimaging (MRI)		X		X		
Blood Draw		X		X		X
Falls Calendar ^^		X		X	X	X

* These tests are implemented to harmonize with inclusion criteria for COMPASS-ND and are not mandatory if the MoCA score ≤ 24 .

** Testing included in the ADAS Cog Plus.

^ 6MWT can be completed at the Baseline Visit or at Day 1 of intervention sessions at the gymfacilities. Please note date and location of the 6MWT in patient file.

^^ Calendar will be given to participant to complete and will be submitted to Research Staff at exercise training.

1
2
3
4
5
6
7

Statistical Analysis Plan (SAP)

10
11
12
13 **SYNchronizing Exercises, Remedies in Galt and Cognition (SYNERGIC) Trial**

13 SYNchronizing Exercises, Remedies in Galt and Cognition (SYNERGIC) Trial

14
15
16
17
18
19
20
21
22
23

Version: Final

Authors: [name], PhD, University of Western Ontario
[name](c), University of Western Ontario
[name], Parkwood Institute
[name], University of Western Ontario and Robarts Research Institute
[name], University of Western Ontario

Date: Sept 2022

24
25
26
27
28
29
30

31 1. Introduction

32 The SYNERGIC TRIAL (SYNchronizing Exercises, Remedies in Galt and Cognition) is
33 a randomized, phase II, fractional factorial, five-arm, double-blind controlled study
34 evaluating the effect of aerobic-resistance exercise with and without cognitive training

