	WAIS III digit forward and backward
	Category fluency – Animals and Vegetable

119 **9. Secondary Outcomes^{*}**

120 Secondary outcomes include neuropsychological assessments, gait and mobility
121 outcomes (including incidence of fall), neuroimaging, and blood biomarkers. *Note that
122 secondary outcomes will be not reported in the primary manuscript.

123 **9.1 Change in cognitive function on neuropsychological tests**

124 The secondary cognitive outcomes will include:

125 a) Montreal Cognitive Assessment test for global cognition
126 b) The ADAS-Cog Recall word list for verbal semantic memory
127 c) Trail Making Test A and B
128 d) Digit Symbol Substitution Test
129 e) Digit Span Test Forward and Backwards
130 f) Boston Naming Test
131 g) Verbal fluency Animals and Vegetables

132 **9.2 Change in gait performance**

133 Gait performance will be evaluated using gait speed and gait variability under single and
134 dual-tasking. Gait speed will be measured as the time taken to walk 6 m using an
135 electronic walkway system (ProtoKinetic® and/or GAITRite® Systems, Inc.). Gait
136 variability of spatial and temporal gait variables (stride time, stride length, double
137 support time and step width) will be calculated using the coefficient of variation (CV =
138 (standard deviation / mean) ×100).

139 **9.3 Change in mobility and falls**

140 Mobility will be measured with the Short Physical Performance Battery (SPPB), and the
141 6 min walk test (6MWT).

142 A fall will be defined as 'unintentionally coming to rest on the ground, floor, or other
143 lower level and not due to a seizure, syncope, or an acute stroke'. Recurrent falls are
144 defined as 'two or more events in a 12-month period'. Falls will be recorded throughout
145 the 12-month trial, participants will be provided with a falls calendars, on which they will
146 record any falls that have occurred, and they will be asked to bring them monthly to the
147 training sessions to review with a research staff member. After the completion of the
148 intervention, participants will be contacted at month 9 and 12 to report incidental falls.

149 **9.4 Change in Neuroimaging**

150 Pre-post regional patterns of brain plasticity will be assessed using structural (high-
151 resolution 3D T1-weighted images = 7 min) in order to get voxel-based volumetric and
152 cortical thickness measures, as well as diffusion tensor imaging (DTI, 30 directions, with

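### Falls calendars are handed in and reviewed at exercise training, which contradicts the protocol's rule that blinded assessors obtain all secondary outcomes on non-training days

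*Combined protocol and SAP*

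**What the plan says.** Falls are a named secondary outcome in both documents. Protocol 4.2 lists "gait and mobility outcomes including incidence of fall", and SAP section 9 lists "outcomes (including incidence of fall), neuroimaging, and blood biomarkers".

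Protocol 5.1 sets the rule for collection: "All primary and secondary outcomes will be obtained and analyzed by blinded assessors on different days to the training programs". Protocol 7.2.2 repeats the blinding part: "Research personnel performing the outcome assessments will be blinded to group allocation".

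The falls procedure reads differently:
- Protocol 6.1 has participants bring their falls calendars to the training sessions.
- The falls-calendar footnote, worded alike in protocol Appendix I and SAP Table 1, says: "Calendar will be given to participant to complete and will be submitted to Research Staff at exercise training".
- SAP 9.3 has participants "record any falls that have occurred, and they will be asked to bring them monthly to the" training sessions, where a research staff member goes through them.
- Of the telephone follow-up at month 9, protocol 7.4 says: "This will be done by the study Site Coordinator or Research Assistant".

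On who delivers training, protocol 6.3 says: "All physical exercise training will be fully supervised by research assistants trained in exercise physiology or with kinesiology or physical therapy backgrounds or training". No falls passage states that the person reviewing calendars or making the call is blinded, or is not one of the training staff.

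**The concern.** The calendar review breaks both halves of the 5.1 rule. It takes place at training, so it is not on a different day. It also takes place where the exercise programme is in view, so the reviewer cannot be assumed blind to the exercise condition.

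Knowledge of the arm matters because a calendar entry is not yet an outcome. SAP 9.3 counts an event only if the descent to the ground or a lower level was unintended and was not caused by seizure, fainting or acute stroke. Someone has to judge intent and cause, and borderline entries can be settled differently in different arms.

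The comparison at stake is falls in arms 1-4 against arm 5. If the result were reported as collected by blinded assessors, that statement would not match the documented procedure.

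**Working it through.** The plan gives no fall rate, no falls power calculation and no falls analysis (SAP 10.3 defers the secondary analyses), so there is no figure to reproduce. The main check is a comparison of passages.

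1. **When.** Rule (5.1): not on training days. Procedure (6.1, Appendix I, SAP Table 1, SAP 9.3): at training. These cannot both hold, whoever the reviewer is.

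2. **Who.** Rule (5.1, 7.2.2): blinded assessors. Procedure (SAP 9.3, 7.4): a research staff member at training, then a Site Coordinator or Research Assistant by telephone. Blinding is not stated for either. Research assistants also supervise exercise (6.3) and give the cognitive-training instructions (6.1.1). This is an overlap of job titles. The documents do not show that the same people do both jobs, and nothing keeps the jobs apart.

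3. **Which comparisons.** Exercise type is visible at a session, so exercise versus arm 5 is exposed. Vitamin D has a matching placebo (6.1.3, 6.2.2), so handling capsules or calendars does not reveal it. ADAS-Cog is measured at the assessment visits by blinded assessors (section 7) and does not use this route.

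4. **How much of the window.** Training runs 20 of 52 weeks: 20/52 = 0.385, or 38%. If the month-9 caller is also unblinded, exposure extends to 9/12 = 75%. The falls calendar is also marked at the 6- and 12-month visits (Appendix I, SAP Table 1), where assessors are blinded.

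5. **What a given error would do (illustration only).** Assume that falls are spread evenly over 12 months, that the true rate ratio is 1.0, and that a fraction q of exposed falls is left out in one exercise condition only. Let f be the exposed share. The observed ratio of arms 1-4 to arm 5 is 1 - fq if the omission is in arms 1-4, and 1/(1 - fq) if it is in arm 5. Neither the values of q nor the even spread comes from the documents.

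| Exposed share f | q = 0.10 | q = 0.20 |
|---|---|---|
| 20/52 (training only) | 0.96 or 1.04 | 0.92 or 1.08 |
| 9/12 (through the month-9 call) | 0.925 or 1.08 | 0.85 or 1.18 |

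For example, with f = 20/52 and q = 0.20: fq = 0.077, 1 - 0.077 = 0.92, and 1/0.923 = 1.08. Applying q to every fall (f = 1) would give 0.80-0.90 or 1.11-1.25. That overstates the exposure, because falls after month 9 are reported at month 12, when neither the training route nor the month-9 call applies.

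**The case against.** The strongest defence is that handing in calendars at training is logistics. Participants record their own falls, the procedure is the same in every arm, 5.1 plans equal trainer contact, and the calendar also appears at the blinded 6- and 12-month visits. Protocol 7.2.2 could be read as covering the falls reviewer too. Much of this stands: it makes unequal recording a possibility and not a finding. It does not remove the conflict, because SAP 9.3 describes a review with staff at the session and not only a hand-in.

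A reader might infer more than the documents support:

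- **That trainers classify the falls, or that the month-9 caller knows the arm.** Only job titles overlap, and by month 9 no training group is in view.
- **That arms 1-4 train upright while arm 5 sits, so that in-session falls must differ.** Three of the five circuit exercises in 6.1.2 are named as seated, and cycling and rowing are allowed. The mainly seated control appears only in protocol 6.2.3, whereas SAP sections 1 and 4 describe balance and toning. Those two descriptions of the control need reconciling, but they do not establish the contrast.
- **That in-session falls should leave the main comparison.** A fall during assigned exercise may be a consequence of that exercise. Removing it could hide a harm and favour the exercise arms.

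Monthly review also has a real merit: in participants with MCI, waiting for the 6-month visit would lengthen recall.

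**Conclusion.** The contradiction is in the text and needs no assumption: a named secondary outcome is handled at training, against the protocol's own rule on who obtains outcomes and when. The consequence is a risk of differential ascertainment in the falls comparison of exercise with arm 5, mainly over the 38% of the window that is supervised training. It reaches further only if the month-9 caller is unblinded, which the documents leave open.

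It would go too far to say that the falls result is biased, or biased in favour of exercise. Neither direction nor size follows from the documents, and the ratios under the working depend wholly on assumed omission rates. The importance is moderate. Falls are one of several secondary outcomes, are kept out of the primary manuscript (SAP section 9) and have no analysis specified yet. The rules can therefore still be settled before that analysis is written.

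**What to change.** - Keep the monthly calendar return, so that recall does not lengthen, but limit staff at training to collecting the calendars.
- Have the existing blinded outcome assessors classify each reported fall against the SAP 9.3 definition. They would work from the calendars and clarify entries by telephone or at the 6- and 12-month visits.
- In protocol 7.4, assign the month-9 call to a blinded assessor.
- Amend protocol 6.1, protocol 7.4, the Appendix I and SAP Table 1 footnotes, and SAP 9.3 so that they agree with protocol 5.1.
- Record whether each fall happened during a supervised session. Keep all falls in the main intention-to-treat comparison and add a sensitivity analysis without the in-session falls.
- If collection is already complete, reclassify the retained fall records masked to arm, and do not describe the falls outcome as collected by blinded assessors.

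The cost is wording changes and a little more assessor time. No new staff role or visit is needed.

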8. ANALYSIS

Analysis, planned analysis, frequency of analysis, and correction for multiple testing

Analysis will be conducted as intention to treat and as per-protocol analysis. For the primary endpoint (ADAS-Cog plus), the change from baseline to six months and 12 months will be assessed using a repeated measures analysis of covariance (ANCOVA) model incorporating the baseline values as covariates. Observing a statistically significant difference in the primary outcome will be considered preliminary evidence of efficacy. Additionally, reduction of prevalence rate of abnormal ADAS-Cog plus score (dichotomous variable) will be assessed as a primary outcome.

We will also report variances, co-variances, and effect sizes, as well as sampling feasibility (i.e., ease of recruitment, recruitment rate, withdrawal rate). Descriptive statistics for demographic and baseline characteristics will be provided with means and standard deviations, or medians and the interquartile range where appropriate, for continuous characteristics and frequencies and percentages for categorical variables.

If the within-group comparison is statistically significant, Tukey's multiple comparisons will identify significant pairwise differences. Similarly, for the secondary endpoints, six month changes in gait performance and secondary cognitive outcomes of interest will be performed using one way analyses of variance. For group comparisons that are statistically significant, pairwise comparisons will be made using Tukey's multiple comparisons tests. All statistical tests will be two-tailed, and a *p*-value of less than 0.05 will be considered to indicate statistical significance. All calculations will be made using SPSS software package version 23.0 (SPSS Inc., Chicago, IL).

Secondary analyses will be also performed according to an intention-to-treat principle and per protocol analysis. Frequency of the analyses: preliminary analysis will be performed at month 6 to ascertain descriptive characteristics at baseline assessment. Final efficacy analysis will be performed at the end of the trial since no safety issues are involved in this study. The statistical significance of the results will be

determined by Hochberg's variation of the Bonferroni procedure for multiple testing.³⁹ An economical analysis will be also performed addressing health resources utilization.

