153 AP/PA correction scan = 7 min) to calculate fractional anisotropy and diffusivity in white
154 matter tracts as well as derive tract-based statistics. Cerebrovascular integrity and
155 pathology will be assessed using the following contrasts: PD/T2 = 5 min; FLAIR = 7 min,
156 and T2* = 5 min). Functional magnetic resonance imaging at rest (rsfMRI plus field map
157 = 12 min) will also be acquired to measure change in data-driven functional networks.

158 **9.5 Change in Blood biomarkers measures**

159 Serum biomarkers of inflammation (C reactive protein, and interleukin 6), neuroplasticity
160 (brain-derived neurotropic factor), endothelial health (vascular endothelial growth factor
161 1), and vitamin D serum levels will be measured before and after intervention.

162 **9.6 Covariates**

163 Pre-specified covariates will be age, sex, years of education and number of
164 comorbidities.

165

166 **10. Statistical Analysis**

167 **10.1 Descriptive Analysis**

168 The baseline characteristics will be summarized using means and standard deviation, or
169 medians and interquartile range where appropriate, for continuous characteristics, and
170 frequencies and percentages for categorical variable.

171 **10.2 Primary Efficacy Analysis**

172 The primary analysis will be based on the intention-to-treat principle, including everyone
173 who were randomized. Comparisons between arms will be conducted according to pre-
174 specifications in the protocol. These comparisons align well with the recommended
175 analysis and reporting of factorial trials⁵, which used “inside the table” and “at the
176 margin” analyses for different comparisons. The “inside the table” analysis will be used
177 to compare each intervention effect to control, while “at the margins” analysis will be
178 used to assess the effect of adding intervention.

179 The major interest would be the effect of the intervention on change in primary
180 outcomes at 6 Month compared to the control arm (arm 5). The primary outcome
181 measure of mean change in ADAS-Cog-13 and ADAS-Cog-Plus scores will be analyzed
182 using a linear mixed model with restricted likelihood estimation. The model will be fitted
183 with participant-specific random intercept and fixed effects of time, intervention arm, and
184 time x intervention arm interaction. The time variable will be used as a categorical
185 variable (0 = baseline; 1 = Month 6.) The intervention arm variable will be dummy

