186 coded, using the control group as a reference category. The interaction term will be

187 used to assess between-group differences (representing a mean difference in change in
188 cognitive scores over time between two groups). With dummy coding of the intervention
189 arm, the interaction term will allow to compare the mean change in each intervention
190 arm to the arm 5 (control). The within-group difference (representing a mean change in
191 cognitive scores over time within the group) will be measured with marginalized mean
192 from the linear mixed regression model. The model will be further adjusted for
193 participant characteristics including age, sex, education, and comorbidities.

194 An unstructured covariance matrix will be used for all models. The model assumption
195 will be assessed using the normal quantile plots of residuals for normality and the
196 residuals vs. fitted plot for variance homogeneity. If the assumptions are not fully met,
197 the data will be transformed (i.e., log). Missing data will not be imputed and will be
198 assumed to be missing at random, as the mixed model approach is well-known to
199 handle such data effectively.⁶ The baseline data from individuals who did not complete
200 Month 6 assessment will be included in the linear mixed model.

201 The mean difference between groups will be presented with their 95% CI and p-value,
202 while the mean change within group will be presented with their standard error. The
203 obtained marginalized mean and standard deviation will be used to calculate the effect
204 size (
$$\frac{\text{mean change in treatment } X - \text{mean change in treatment } Y}{\text{pooled standard deviation of change}}$$
). As outlined in our published
205 protocol, we will calculate the proportion of participants with improvement in primary
206 outcomes.

207 All tests will be two-sided, and p-value of less than 0.05 will be considered as
208 statistically significant. Adjustments for multiple comparisons will not be made as the
209 trial is intended to compare the intervention effect to the control rather than pairwise.⁷
210 Per-protocol analysis will be performed as well.

211 As per recommended analyses of fractional factorial design⁸, “at the margin” analyses
212 will be performed by collapsing arms according to the pre-specified comparison.
213 Collapsing intervention arms allow to increase the study power to detect the difference

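### SAP 10.2 replaces the protocol's baseline-adjusted analysis with a model that leaves a free arm effect at baseline, which gives up some precision without a stated reason

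*Combined protocol and SAP*

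**What the plan says.** **Protocol section 8 (Analysis).** The primary endpoint is assessed by a repeated measures ANCOVA, a "model incorporating the baseline values as covariates".

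**SAP 10.2.** Time is coded 0 for baseline and 1 for Month 6, so the baseline score is an outcome row. The model is fitted "with participant-specific random intercept and fixed effects of time, intervention arm, and" their interaction. The interaction is "used to assess between-group differences (representing a mean difference in change in" score. "The model will be further adjusted for" age, sex, education and comorbidities; the baseline score is not on that list. On covariance the SAP says: "An unstructured covariance matrix will be used for all models".

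**The SAP's reason for a mixed model.** Missing data are not imputed and are "assumed to be missing at random, as the mixed model approach is well-known to" deal with them. "The baseline data from individuals who did not complete" Month 6 also enters the model.

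SAP 10.2.1 to 10.2.3 refit the model with collapsed arms, and 10.2.4 uses it as it stands. SAP 10.2 adds: "Per-protocol analysis will be performed as well".

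**The concern.** With two visits and a separate baseline mean for each arm, the time-by-arm coefficient is a difference in mean change. Chance differences between arms at baseline are subtracted in full, whatever the correlation between visits. An analysis that adjusts for baseline, or that uses the fact that randomised arms share a baseline mean, removes only the part of the baseline difference that predicts Month 6. It is usually more precise.

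The listed covariates do not restore the adjustment. As main effects that do not vary over time, they leave the interaction estimate unchanged when everyone has both visits.

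At stake is the width of every Month 6 confidence interval, including the comparisons with arm 5, which SAP 10.2 treats as the main interest and which have the least power.

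**Working it through.** **Inputs from the documents.** SAP section 7: 40 per arm, 15% attrition, d about 0.5 on change in ADAS-Cog-13, 80% power. SAP 10.2: two-sided 0.05. Hence 40 × 0.85 = 34 completers and 6 baseline-only participants per arm.

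**Assumed, because the documents do not give them.** Correlation rho between baseline and Month 6 of 0.5 to 0.9; Month 6 SD equal to baseline SD (k = 1), relaxed in step 5; Month 6 scores missing at random.

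**1. The SAP's own figure.** n per group = 2(1.96 + 0.842)²/0.5² = 63 (64 with the t distribution). For two arms against two arms that is 32 per arm, and 32/0.85 = 38, close to the planned 40. So 80% is met for the two-arm margins. On a plain change score in completers (noncentral t), power is 82.5% for 68 v 68, 73.7% for 136 v 34 and 52.9% for 34 v 34.

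**2. What the SAP contrast is.** In a simulated complete data set, the REML interaction estimates equalled the raw differences in mean change to five decimals in all four arms, with age in the model as a main effect. ANCOVA on the same data gave different values.

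**3. Variance with 34 completers and 6 baseline-only per arm**, baseline SD = 1, covariance known:

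- Completers' raw change, per arm: 2(1 − rho)/34
- SAP model, per arm: (1 − rho²)/34 + (1 − rho)²/40
- Common baseline mean, per-arm contribution to a contrast: (1 − rho²)/34
- Common baseline / SAP = (1 + rho)/[(1 + rho) + 0.85(1 − rho)]

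For rho = 0.5 the last line is 1.5/(1.5 + 0.425) = 0.779; for rho = 0.9 it is 1.9/(1.9 + 0.085) = 0.957.

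| rho | SAP / completers' raw change | Common baseline / SAP | Interval narrower by |
|---|---|---|---|
| 0.5 | 0.9625 | 0.779 | 11.7% |
| 0.7 | 0.9775 | 0.870 | 6.7% |
| 0.8 | 0.985 | 0.914 | 4.4% |
| 0.9 | 0.9925 | 0.957 | 2.2% |

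The ratios are the same for single-arm and collapsed contrasts, because completers and baseline-only participants stay in the same proportion. Simulation with 15% of Month 6 scores missing at random agreed: ANCOVA / SAP-type model = 0.77, 0.88, 0.92 and 0.96.

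**4. Power**, noncentral t, df = n1 + n2 − 2. The effect in SD units is 0.5 divided by the square root of the variance relative to completers' raw change: column 2 above for the SAP model, (1 + rho)/2 for the common baseline.

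| Contrast | SAP model, rho 0.5 / 0.9 | Common baseline, rho 0.5 / 0.9 |
|---|---|---|
| Arms 1-4 v arm 5 (136 v 34) | 75.3% / 74.0% | 84.9% / 75.8% |
| Single arm v arm 5 (34 v 34) | 54.4% / 53.2% | 65.0% / 55.0% |
| Two arms v two arms (68 v 68) | 83.9% / 82.8% | 91.7% / 84.4% |

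Arms 1-4 against arm 5 reaches 80% only if rho is about 0.71 or lower.

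**5. Unequal variances.** With k = Month 6 SD / baseline SD, the step 3 ratio becomes k²(1 − rho²)/[k²(1 − rho²) + 0.85(1 − rho·k)²].

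- rho 0.9, k 1.1: (1 − 0.99)² = 0.0001, ratio 0.9996, no useful gain.
- rho 0.8, k 1.25: rho·k = 1, ratio exactly 1.
- rho 0.7, k 1.2: 0.7344/(0.7344 + 0.0218) = 0.971, interval 1.4% narrower.
- rho 0.7, k 0.9: 0.4131/(0.4131 + 0.1164) = 0.780, interval 11.7% narrower.

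The added denominator term is a square, so the ratio never exceeds 1. Estimating the slope costs about one degree of freedom.

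**The case against.** The SAP is coherent on its own terms. It defines the outcome as change, sizes the trial on change and standardises effects by the SD of change; the interaction matches all three. It gives a reason for the mixed model, and nothing about the analysis is invalid. The two-arm margins exceed 80% power either way, and single-arm comparisons stay well below it either way. This makes the point an efficiency improvement rather than a threat to a conclusion.

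Most of that stands. The stated reason does not, however, explain the free baseline effect: a common-baseline model keeps the same participants under the same missing-at-random assumption. Keeping them lowers the SAP contrast's variance by only 3.8% to 0.8% relative to completers' raw change.

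A reader might infer more than the documents support:

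- **Bias or inflated type I error.** Neither follows under randomisation.
- **The model as the cause of low power against arm 5.** The 34-person control arm is the cause; adjustment offsets it only in part.
- **A larger gain**, such as intervals 13% to 2.5% narrower, from the complete-data ratio (1 + rho)/2. That compares with completers' raw change, not with the SAP model, which also uses baseline-only participants.
- **A guaranteed minimum gain.** Step 5 shows there is none.
- **A choice made after seeing results.** The documents do not state the blinding status at the SAP date.

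**Conclusion.** The point holds as a loss of precision and an unexplained departure from protocol section 8. Equality with raw change is exact only on complete data; with the planned attrition it is close. The variance reduction of about 22% to 4% rests on equal variances at the two visits and on an assumed rho of 0.5 to 0.9. It is larger if the Month 6 SD is below the baseline SD and can fall to about zero if it is above. Apart from about one degree of freedom, adjustment does not cost precision. Only arms 1-4 against arm 5 could cross 80% power because of it, and only at the lower correlations. The change is worth making because it uses a score already scheduled, but confidence in its size is moderate.

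**What to change.** In SAP 10.2 and the collapsed-arm analyses, for the intention-to-treat set:

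1. Drop the arm main effect so that all arms share one baseline mean: time plus time-by-arm, with an unstructured residual covariance and no separate random intercept, which is redundant with two visits. Say that the unstructured matrix is the residual one. Baseline-only participants stay in.
2. Report ANCOVA of Month 6 on the baseline score as a sensitivity analysis. Use it as the per-protocol form, since randomisation does not guarantee a common baseline in that set.
3. State that within-group changes and the inputs to the effect size will come from the new model.
4. Document the change as made before any unblinded analysis.

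If the present model is kept, say why baseline adjustment was dropped. Site-by-time and covariate-by-time terms are optional; no gain from them has been shown here.

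The cost is SAP wording, model code and about one degree of freedom, with no new participants, visits or measurements.
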